10.6.3 Table 4: Summary of Intervention Provider Roles and Timing of Patient Contacts

Team member	PCP	NCM	Telephone Health Coach
Role and responsibilities	
 Brief advice Discusses opioid use in context of overall health 	
 Health education Risk reduction counseling Overdose prevention and naloxone provision Self-management skills Education on non-pharmacologic pain management Referrals and support for pain, mental health, SUD treatment, other services. Supports engagement in primary care Uses motivational enhancement strategies to engage patients in SUD treatment when indicated 	
 Offers support Risk reduction counseling Suggests strategies for overcoming barriers Enhances motivation for behavior change Encourages engagement w/ primary care and behavioral health providers in the clinic Encourages utilization of community and/or on-line resources to support behavior change 
Enhanced coaching:
 
 Evidence-based counseling (MI/CBT) focused on substance use behavior change
Timing of patient contacts	
 Baseline visit or within 10 business days Readdress in follow-up primary care visits 	
 Baseline visit Ongoing monitoring and engagement in conjunction with PCP. Meets on an approximately monthly basis for patients prescribed chronic opioids and as needed for all patients 	
 Telephone Health Coaching: Week 2 and Week 4 (approximately) following baseline visit Enhanced coaching: For individuals who may benefit from further intervention: Weeks 7,8,9,10 (approximately)
Location	Clinic, telehealth, or telephone	Clinic (contacts are in-person +/- by telephone)	Telephone and/or video

Nurse Care Manager

The Nurse Care Manager (NCM) is a central element of the intervention, as the nurse works closely with the PCP to assess, educate, and manage patient participants with risky opioid use. For all patient participants in the STOP condition, it will include facilitating linkage to needed specialty care, including pain (e.g., physical therapy), mental health (pharmacotherapy) and addiction, as indicated. NCMs will provide health education and counseling on risk reduction, overdose prevention and self-management skills. For patient participants on COT, the role will include monitoring opioid prescribing and risks. Details of the NCM intervention are outlined in Table 5 below. Patient participants will be asked to participate in an initial visit with the NCM, which will occur on the same day as the baseline visit if possible. The NCM continues working with patients in the STOP condition throughout their 12 months of study participation. Following the initial visit with the NCM, the frequency of visits depends on patient participant needs. For all patients of intervention PCPs, the NCM can provide care management and usual nursing care. For all patients of PCPs in the EUC arm, the NCM cannot provide any care management. They can perform nursing activities distinct from what they do for enrolled intervention patients. For example, they can assist with clinic-wide initiatives such as immunization clinic (e.g., flu shots), or other nursing care (triage, wound dressing, etc.). The NCM may also work with all patients of the clinic who are receiving medication for OUD, as these patients are not eligible for our study.

Table 5: Nurse Care Manager Intervention

Nurse: Patient Participant ratio¹	

 Approximately 50 patient participants/1.0 FTE NCM (panel will increase over the course of the study, as patient participants are enrolled). 	
Roles/Duties	

 Integrating into work flow: Prior to the start of the study, NCM will coordinate with existing practice staff to ensure smooth transition of duties and integration into usual work flow for patients of intervention PCPs. Reviewing panel of patient participants with risky opioid use, including those on COT: Meet with PCP to review patient participant panel to identify high risk or problem patient participants; and as patient participants are enrolled into the study, to review with PCP before or after PCP visit. Review charts and prescription drug monitoring program (PDMP) for presence of treatment agreements, urine drug screens and risk factors. Engage and assess patient participants: Conduct initial and ongoing evaluations for substance use and opioid use disorder, pain, mental health symptoms, social supports, overdose risk, suicidality, and barriers to treatment engagement and adherence. Conduct urine drug testing and pill counts (for patient participants on COT). Educate and counsel patient participants: Provide health education on substance use and disease or symptom self-management, including the relationship of opioid use to pain. Provide opioid risk reduction and overdose prevention counseling, ensure that patient participant is offered naloxone kit and training. Teach self-management skills for pain and other triggers for opioid use. Support engagement in care: Outreach to patients in between scheduled PCP visits or if patient cancels/no shows to visits to offer counseling and support. Refer patient participants to appropriate clinic and community resources, support ongoing engagement in primary care. Meet with PCPs: Review patient participants, help interpret urine drug screen results. Track prescriptions for patient participants and when appropriate, prepare prescriptions for PCPs to sign for naloxone and/or COT. Management of patient participants with substance use disorder: Refer patient participants with any active substance use disorder to treatment within or outside of the practice, as appropriate. Documentation: the NCM will document all patient participant interactions, changes to care and incidents in the EHR as a progress note. Provide care management and usual nursing care to all patients of intervention PCPs. 	
Patient Participant Tracking	

 Each practice will choose an approach to track patient participants with subthreshold OUD. Templates of recommended fields will be supplied by the study. Options include: 1) Use EHR if possible, 2) local database (Excel, Access, etc.), or 3) develop a clinic registry. 	

¹ In addition to study participants, nurses may manage up to 50 patients who are receiving COT or MOUD and have a PCP in the STOP intervention condition but are not participating in the study.

Telephone Health Coaching

The STOP protocol includes one-on-one telephone behavioral coaching targeting risky opioid use. Patient-facing interventions based on Motivational Interviewing (MI) and Cognitive Behavioral Therapy (CBT) will utilize phone follow-ups to improve patient participant motivation and self-efficacy to change health behavior [45-47] and behavioral outcomes.[45, 48] MI and CBT are evidence-based treatments for behavioral health conditions, including opioid and other substance use, and can effectively be delivered via telephone and in as few as 2 sessions, with increased efficacy when up to 4 sessions are delivered. They are commonly integrated to optimize potency.

Consistent with our Social Ecological Framework of Unhealthy Opioid Use, telephone health coaching will target multiple levels that impact subthreshold OUD. These include individual patient factors (knowledge, motivation, self-efficacy, behavioral skills), interpersonal factors (education on communication skills and limit setting), organizational factors (within clinic resource referral), and community factors (community and/or on-line resource referral).

All patient participants in the STOP arm will be offered telephonic health coaching sessions with or without video at approximately 2- and 4-weeks post-baseline. Patient participants who may benefit from additional coaching (for example, those who do not improve or who experience clinical worsening of unhealthy opioid use) may receive up to 4 additional coaching sessions from the telephone health coach. Coaching is delivered from a centralized call center, by staff that receive standardized training and supervision. To the extent possible, calls will be scheduled at the patient participant's convenience (e.g., evenings, weekends). Patients may chose not to participate in health coaching.

Basic Coaching (Step 1):

All patient participants in the STOP arm will be offered the Step 1 coaching, which is conducted by telephone health coaches, who are trained health professionals. The coaches will assess the patient participant's current opioid use and other needs and provide appropriate referrals and resource links. The coaching approach is supportive and informed by MI techniques, which seek to increase the patient participant's motivation and self-efficacy to improve health behaviors.

The content of the Step 1 coaching focuses on the domain areas of substance use behavior, stress/mood management, and quality of life issues, with a particular emphasis on risky opioid use and overdose prevention. Sessions will be tailored to address risky use of other substances and provide brief recommendation to quit/reduce risky opioid use. For patient participants who endorse readiness to change, coaching will address behavioral skills acquisition, as well as behavior change plan development and implementation. Telephone health coaches will make referrals to clinic social work/behavioral health or other clinic services, or referrals to clinic/community resources, in response to barriers to opioid use reduction raised by patient participants or need for additional services. Timing of coaching sessions will be based at the patient participant's convenience, including evenings and weekends. Patient participants will be given approximately \$3 per completed call for reimbursement of cell phone costs.

Step 1 coaching will include 2 sessions, each 20 to 30 minutes in length. The first will occur approximately 2 weeks post-baseline and the second will occur approximately 4 weeks post-baseline. While these are ideal windows, if initial attempts to complete the counseling sessions are unsuccessful, further attempts to engage patient participants will be made for up to 3 weeks after the target date for each call.

Enhanced Coaching (Step 2):

Patient participants who may benefit from additional coaching following the Step 1 sessions will be offered up to 4 additional sessions with a telephone health coach. Patient participants will be referred for these coaching sessions by the NCM or PCP, or at the discretion of the telephone health coach, based on clinical criteria which may include ongoing or escalating nonmedical or illicit opioid use, overdose risk behavior, symptoms of OUD, OD episodes, and/or consequences of opioid and other substance use. This determination will typically be made during or after the first or second Step 1 coaching session. These criteria will be further detailed in the MOP, and training on their application will be provided as specified in the training plan.

The telephone health coach will provide patient participants with approximately 4 sessions of coaching over the telephone for Step 2. Calls with or without video will occur approximately weekly and each call will be approximately 30-40 minutes in length. An assessment of motivation to reduce risky opioid use will be conducted by the clinician using MI-based “rulers” (e.g., “On a scale of 0 to 10, how motivated are you to reduce your risky opioid use right now?”). For patient participants with low motivation to change current unhealthy behaviors, the coach will conduct additional MI to increase motivation and self-efficacy. As patient participants increase readiness to change, specific behavioral strategies for relapse prevention and pain self-management will be presented by the coach within a CBT framework. These coaching sessions will ideally start within two weeks of the patient participant’s referral into Step 2 and occur once a week for four consecutive weeks. Circumstances in which a participant may receive more or less than 4 sessions (for example, the participant refuses further coaching, or is unable to fully complete one of the sessions and wants to schedule a make-up to receive the intended content) will be detailed in the manual of procedures. If initial attempts to initiate the telephone health coaching sessions are unsuccessful, further attempts to engage participants will be made for up to 10 weeks after the referral. This time period reflects usual care practices in terms of being able to re-engage with care at a later time, balanced against the need to deliver the treatment prior to assessing outcomes in the study. Following the initial session, the subsequent 3 coaching sessions will ideally be completed weekly (one session/week). If one of these sessions is missed or delayed, further attempts to re-engage the patient participant will be made for up to 3 weeks after the target date for each session. Timing of calls will be based at the patient participant’s convenience, including evenings and weekends. Patient participants will receive approximately \$3 per call for reimbursement of cell phone costs.

10.7 Premature Withdrawal of PCP or Patient Participants

10.7.1 Withdrawal of PCP Participants

All PCP participants will be followed for the duration of the study unless they withdraw consent, or the investigator or sponsor decides to discontinue their enrollment for any reason. PCP

participants may withdraw voluntarily from the study at any time. Reasons for the investigator or sponsor terminating a PCP participant from the study may include, but are not limited to, the PCP breaking the study blind, lack of funding, or DSMB early termination of the study for safety or effectiveness reasons.

10.7.2 Withdrawal of Patient Participants

All patient participants will be followed for the duration of the study unless they withdraw consent, die, or the investigator or sponsor decides to discontinue their enrollment for any reason. Patient participants may withdraw voluntarily from the study at any time. Reasons for the investigator or sponsor terminating a participant from the study may include, but are not limited to, the patient participant becoming a threat to self or others, lack of funding, or DSMB early termination of the study for safety or effectiveness reasons. Treatment will be discontinued if there is evidence that continuing in the study would be harmful to the patient participant. Patient participants who withdraw or discontinue early may be replaced with other eligible individuals, if the site is still in the enrollment phase.

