10.10.2 Maintenance of the Blind

Most assessments are self-administered (SA) by patient participants. It is not feasible to blind research staff because the delivery of some intervention components require their involvement (e.g., showing educational video vs. video doctor to the participant, intervention specific CRFs). Patient participants may be able to deduce the assignment of their PCP, (e.g., through conversation with other patient participants in the study), but this information will not be

volunteered by clinical or research staff. To assess the success of the blind, patient participants will be asked at the end of the study what they considered to be the goal of the research.

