The Demographics form collects information about demographic characteristics of the participant, including biological sex, date of birth, ethnicity, race, education, employment status, and marital status. Self-reported information on insurance status will also be collected. To minimize assessment reactivity, only those substance use assessments that are required to inform primary and secondary outcome measures are collected. We will adopt PhenX toolkit items for collecting these measures to the extent possible, but will not include the full battery of the Substance Abuse and Addiction Collection of the PhenX Toolkit (<http://www.phenxtoolkit.org/>).

11.3.1.4 *Study Completion Form*

This form tracks the participant's status in the study. It is completed at the month 12 follow-up visit, or once the month 12 follow-up visit window lapses for participants who do not complete this final follow-up. If the participant withdraws consent, dies or is removed from the study per judgement of study staff, this form will be completed at the time of termination from the study. This form is used in data analyses to address variables such as treatment retention and completion. This form also provides a location for the site PI attestation of review of all study data.

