4.2.4 Visit Attendance

The number and percentage of patient participants attending the five study visits will be summarized at baseline and at 3, 6, 9, and 12-months post-baseline by treatment arm. Information on missed visits during the study will be presented by treatment arm, including the number of missed visits, the number of patient participants with at least one missed visit, and the reasons for the missed visits. The expected number of study visits is calculated based on the general rule that five total visits are expected per patient participant. The average number of missed visits per patient participant will be calculated by dividing the number of missed visits by

the number of patient participants. For early study terminations, visits are only considered missed during active study participation if they occur before the study termination date.

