 - It is assumed that patient participants who drop out will have higher use after their dropout date than those who remain in the study, that is, that days of use after the withdrawal timepoint for dropouts in the treatment arm may more closely resemble that of controls than that of other treated patient participants. The values of missingness due to dropout might not retain the trend of prior observations since they are not exposed in the study environment due to various reasons, therefore the mechanism of missingness is assumed missing not at random (MNAR).

For the imputation of the primary outcome, two separate imputation procedures will be used to complete the imputation process for intermittent missingness and dropout. In the first step, the MI procedure statement uses the Markov Chain Monte Carlo (MCMC) method to impute the values of missing outcomes from intermittent missingness under the missing assumption of MAR. The variables specified in the mixed-effect regression model in Section 7.2.2, are included for imputation of primary outcome. The SAS code for imputing missing data from intermittent missingness is given below.

```
/* imputing the intermittent missingness with MAR assumption */
PROC MI DATA=datamiss nimpute=30 OUT=outimp1 SEED = 100623
min=. . 0 0 0 0 0 0
max=. . 30 30 30 30 30 30;
by treat;
mcmc impute=monotone;
VAR treat site baseline daysinmon1-daysinmon6;
RUN;
```

In this step, this MI procedure produces 30 imputed datasets by filling in the missing values from intermittent missingness with statement “impute=monotone”, and then produces the datasets as monotone missingness. The missing values due to intermittent missingness are imputed assuming that the intervention effect is still carried out while they remain enrolled in the study.

Next, MI procedure is to impute missing values from the dropouts under assumption of missing not at random (MNAR), which is a control-based pattern imputation assuming that after dropout, the unobserved values in the intervention group follow the path of observed values in control group. Based on this assumption, only the observed values in EUC group are used to derive the posterior distribution of the parameters from which the missing values in both EUC and STOP group are imputed. This approach is conservative as it tends to reduce the difference between STOP group and EUC group. The SAS code for imputing missing data from dropout is given below.

```

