8.2 Suicide Risk

The questions 'Over the past 2 weeks, have you had thoughts of killing yourself?' and 'Have you ever attempted to kill yourself? If yes, when did this last happen?' are asked on the Patient Safety Screener (PSS) assessment at baseline, 6-months, and 12-months. A response of 'yes' to having suicidal thoughts over the last 2 weeks or 'yes' to attempting suicide within the last 24 hours (including today) or within the last month (but not today) indicates potential suicide risk.

A summary table of the number of patient participants endorsing suicidal ideation at baseline, 6-months, and 12-months, as well as the number of patient participant endorsing suicidality at either 6 or 12-months, will be presented by treatment arm. A listing for all visits for patient participants endorsing suicidality at least one visit will be presented by treatment arm. The listing will include Site, Participant ID, date of enrollment, visit, date of assessment, and the questions 'Over the past 2 weeks, have you had thoughts of killing yourself?' and 'Have you ever attempted to kill yourself? If yes, when did this last happen?' from the PSS assessment.

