Table 15: Proposed and Actual Enrollments by Site

Patient Participants

Site	Proposed Enrollments¹	Date Site Opened for Enrollment	Date of First Enrollment	Actual Enrollments	Actual/Proposed (%)	Date of Last Enrollment
Chase-Breton Health Center	N	mm/dd/yyyy	mm/dd/yyyy	N	X.X%	mm/dd/yyyy
Dartmouth-Hitchcock						
Annville Family Medicine						
University of Utah						
The Ohio State University						
Total						

¹ Proposed Enrollment = proposed number of enrollments per site based on the total sample size N.

**Table 16: Summary of Disposition by Site
Patient Participants**

[figure not shown]
	Chase-Breton Health Center	Dartmouth- Hitchcock	Annville Family Medicine	University of Utah	The Ohio State University	Total
Number of patient participants enrolled	N					
Number of study completers ¹	N (X.X%)					
Number of early study terminations ²	N (X.X%)					
Reason for early study termination						
Participant stopped participation due to practical problems (e.g. no childcare or transportation)	N (X.X%)					
Participant incarcerated						
Participant withdrew consent/assent						
Participant deceased						
Participant terminated for administrative issues						
Participant terminated due to pressure or advice from outsiders						
Participant in hospital, in-patient, or residential treatment (not for substance abuse treatment)						
Clinical deterioration: new onset of psychiatric or medical condition						
Participant in detox, residential, or intensive outpatient treatment for substance abuse treatment						
Participant refused, non-specific						
Unable to contact participant						
Participant terminated due to COVID-19: Illness						
Participant terminated due to COVID-19: Public health measures						
Participant terminated due to COVID-19: Other						
Participant terminated for other reason						

¹ A participant is a study completer if they have a completed Study Completion (STC) form indicating they have completed their last study activity.

² A participant is an early study termination if they have a completed STC form indicating they did not complete their last study activity.

Table 17: Summary of Disposition by Treatment Arm			
Patient Participants			
	Treatment Arm		Total (N=)
	EUC (N=)	STOP (N=)	
Repeat of Table 16 with Treatment Arm for columns			

Figure 4: CONSORT Flow Diagram
Patient Participants

¹ Potential patient participants may prescreen multiple times and therefore may be counted multiple times in this number.

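### Unblinded staff may end a patient's follow-up together with enrollment, and the plan does not provide for collecting self-reported outcomes afterwards

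*Protocol*

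**What the plan says.** Protocol 10.7.2 follows each patient for the whole study with three exceptions: withdrawn consent, death, or that "the investigator or sponsor decides to discontinue their enrollment for any reason". Its examples of reasons for termination include "the patient participant becoming a threat to self or others". The same section speaks separately of discontinuing treatment for harm, but does not say that data collection then continues. It also allows patients who leave early to be replaced while the site is still enrolling.

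Protocol 11.3.1.4 (Study Completion Form) adds that if a participant "is removed from the study per judgement of study staff, this form will be completed at the time of termination from the study". Protocol 10.10.2 explains who makes such decisions: "It is not feasible to blind research staff because the delivery of some intervention components require their involvement".

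On the analysis side:

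- SAP 7.2.3 treats every dropout within months 1 to 6 alike, assuming that "after dropout, the unobserved values in the intervention group follow the path of observed values in control group".
- SAP 7.8 states that secondary outcomes are not multiply imputed.
- SAP 8.2 takes suicide risk from the "Patient Safety Screener (PSS) assessment at baseline, 6-months, and 12-months". SAP 8.1 takes non-fatal overdose from self-report on the same schedule, and the OUD interview follows it too (Protocol 11.4.3).
- SAP 4.2.4 counts attendance so that, after early termination, "visits are only considered missed during active study participation if they occur before the study termination date".
- The disposition table (SAP 18.1, Table 16) offers "Clinical deterioration: new onset of psychiatric or medical condition" as one termination reason, beside hospital stay, substance use treatment and incarceration.

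**The concern.** Stopping the study intervention and stopping data collection are different acts, and the protocol lets one staff decision do both. Some grounds for that decision are themselves trial outcomes or lie close to them: suicidality (H2.12), acute care use (H2.15), addiction treatment (Exploratory Objective 4).

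The chance of removal could also differ by arm. In STOP, the nurse care manager carries out continuing assessments that include suicidality and overdose risk (Protocol Table 5), and coaches ask about suicidal ideation when indicated (12.5). EUC has no study intervention after baseline (10.6.1). The staff know the assignment.

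What is at stake is mainly the self-reported safety and secondary outcomes of the patients who are removed, because these come only from scheduled assessments. The SAP's safety population is everyone enrolled (3.2.9), and Table 66 does not state its denominator. If that denominator is all enrolled patients, a removed patient would count as having no suicide risk. For the primary outcome, months that could have been observed become months to be imputed.

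**Working it through.** **Planning figures.** SAP 10.0, Scenario 1, has 90-day means of 20 (EUC) and 14 (STOP) in both intervals. Over 180 days that is 20 + 20 = 40 and 14 + 14 = 28: a difference of -12 days, as the SAP states, and a ratio of 28/40 = 0.70. The stated power for this scenario with 60 PCPs and 5 patients each is 0.97. Simulation gave 0.968 with the individual intercept redrawn for each interval and 20% random dropout, 0.964 with one intercept and no dropout, and 0.943 with one intercept and 20% dropout. Power does not bear on this point, because the plan's simulations treat dropout only as an assumed 20% loss.

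**What the plan does not give.** Neither document states how many patients staff have removed or expect to remove. The only related figure is up to 20% missing the primary endpoint from dropout and nonresponse together (SAP 7.2.3). Everything below is therefore hypothetical.

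**How the missing months are filled.** The second imputation step in SAP 7.2.3 is a monotone regression on site, baseline and the earlier months, with the model fitted to EUC observations only. A removed STOP patient's later months are predicted from that EUC model, given the patient's own earlier reports. EUC dropouts use the same model. Intermittent gaps are filled separately, by arm, under MAR.

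**Illustration.** Suppose a share f of STOP is removed after month 3 and would truly have had u days of use in months 4 to 6 (assumed). As a simplification, the filled value is the EUC mean of 20, and months 1 to 3 stay at the arm means.

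- Filled ratio = [28 + f(20 - 14)] / 40
- True ratio, removal in STOP only = [28 + f(u - 14)] / 40
- True ratio, same share removed in both arms = [28 + f(u - 14)] / [40 + f(u - 20)]

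| f | Filled | True, u = 14 (like other STOP), STOP only | True, u = 30 to 60, STOP only | True, u = 30 to 60, both arms |
|---|---|---|---|---|
| 2% | 0.703 | 0.700 | 0.708 to 0.723 | 0.704 to 0.709 |
| 5% | 0.708 | 0.700 | 0.720 to 0.758 | 0.711 to 0.721 |
| 10% | 0.715 | 0.700 | 0.740 to 0.815 | 0.722 to 0.741 |

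With removal in STOP only, the sign turns at u = 20. Below the EUC level, filling pulls toward no difference; above it, filling flatters STOP. Because the real imputation uses earlier months, a patient whose heavy use was already visible would be filled above the EUC mean, and the gap would be smaller than shown.

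**Sensitivity analyses.** SAP 7.3 lists a complete-case analysis and imputation under MAR throughout. Neither represents removed patients who do worse than comparable EUC patients.

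**The case against.** The documents mostly respond to bad outcomes by keeping patients in. Endorsing suicidal thoughts at 6 or 12 months leads to a follow-up form under site procedures (Protocol 11.8.1), not removal. Patients who develop OUD are offered care (10.6), no treatment is prohibited (13.1), and people who become prisoners may stay with approval (10.9.1). The threat example in 10.7.2 is permissive. All of this stands, and suggests that removals may be few.

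Part of the loss is also covered. Chart review spans 12 months after enrollment (10.8), and the one stated example of its omission is withdrawn consent (SAP 3.2.5). Overdose death is sought in records for patients not reached at month 12 (Protocol 7.2.1). Exploratory Objective 4 also draws on the health record, and termination reasons are tabulated by arm (SAP 4.2.2, Table 17). This stands too, but none of it replaces the suicide screener, self-reported overdose, the OUD interview or days of use. Whether chart review continues after a staff removal is not stated.

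Several stronger readings are tempting and not supported:

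- A reader might infer that the worst outcomes do go unobserved. The text shows only that they could.
- A reader might take the completion form to close the record, or clinical deterioration to be a removal rule. One is a status form and the other a disposition category.
- A reader might suppose that STOP patients are set to the EUC level and compute a fixed dilution. At 2 days per month, four lost months would be 8 days, and 5% of patients would cost 0.4 of 12 days, about 3%. That gives removed patients average STOP use, which contradicts the worry that they use heavily, and it ignores the conditioning on their own history.
- Greater detection in STOP is an inference. The suicide screener and the timeline follow-back are staff-administered on the same schedule in both arms.

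**Conclusion.** The concern holds in limited form. A stated rule, not just missing detail, lets unblinded staff end enrollment and with it follow-up on grounds that may be related to outcome, and nothing provides for self-report afterwards. The case is strongest for the safety and secondary outcomes that come only from scheduled assessments.

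For the primary outcome the size and direction are unknown. If removed STOP patients resemble other STOP patients, the imputation pulls toward no difference, which SAP 7.2.3 openly calls conservative. If they use more than comparable EUC patients, it flatters STOP. The illustrated gaps rest on assumed removal shares of 2% to 10% for this single cause and on assumed use of 30 to 60 days; they are not estimates for this trial. A reader might conclude that the planned result is biased in a known direction, but the documents do not support that. This is a cheap improvement rather than a flaw that undermines the primary analysis.

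**What to change.** In Protocol 10.7.2 and 11.3.1.4, separate two events: study intervention stopped, and follow-up ended. Leave the rule for stopping the intervention as it is.

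After a staff decision to stop, keep sending the remote monthly surveys and keep offering the remote 6- and 12-month patient-reported assessments. Exceptions are:

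- the patient withdraws consent for data collection;
- the patient dies;
- the study closes;
- prisoner rules (10.9.1, 15.9) forbid contact;
- contact would endanger staff or others.

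State that chart abstraction and the death search are still completed where consent stands. Record the date and reason for stopping the intervention separately from the end of follow-up, and report both by arm.

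The cost is protocol wording, an added date and reason on one form, and a few more survey incentives and staff contacts. If follow-up has already closed, completing chart abstraction and the death search for removed patients, and reporting staff removals by arm and reason, would still be useful.
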